5.0 Amendments and Updates

Number	Date	Section of Study Protocol	Amendment or Update	Reason
11011	16/09/2015	n/a	Initial Protocol	n/a
11011	25/09/2015	Management and Reporting of Adverse Events/Adverse Reactions	Delete Pediatric, Malignancy, and Product Complaints	As per the comments of GMA-RC
11011	01/10/2015	Study size	Sample size calculation	As per the comments of GMA-RC
11011	28/10/2015	Management and Reporting of Adverse Events/Adverse Reactions	Amend the AE collection period, AE reporting and Pregnancy as the protocol standards	As per the comments of GMA safety management Subjects will be contacted approximately 70 days following the intake of the last dose of physician-prescribed treatment for an assessment of any new or ongoing AEs.

6.0 Milestones

Major study milestones and their planned dates are as follows:

Start of Data Collection (FPFV):	10 October 2015
End of Data Collection:	31 January 2017
Database Lock:	28 February 2017
Interim Database Lock:	Nil
Interim Report:	Nil
Final Report of Study Results:	30 June 2017

7.0 Rationale and Background

Disability has been defined as impairments, activity limitations and participation restrictions due to personal and environmental factors (1). The concept of disability is one where a physical health condition or disease is evaluated in terms of its impact, difficulties, or limitations on a range of tasks, activities, or roles that are considered typical of everyday life. Examples of affected activities include basic aspects of daily living such as eating, bathing, dressing, household chores and meal preparation, or participation in society, or participation in work.

For public health purposes disability is becoming increasingly important as an outcome measure. Despite this, there has been no data available, within our knowledge, on the effectiveness of adalimumab on health-related QoL and work productivity in patients with Rheumatoid Arthritis (RA) in Taiwan so far. Results from study of effect of adalimumab on Work Productivity and Activity Impairment (WPAI) scores and other Patient-Reported Outcomes (PROs) of work activity and well-being will be of interest to a variety of stakeholders in the healthcare system including patients, healthcare practitioners and payers in Taiwan.

Reimbursement in Taiwan is strongly influenced by local “real -world” evidence of the intervention’s impact on patient outcomes and economic endpoints. The Bureau of National Health Insurance (BNHI) in Taiwan endorsed Dose Tapering and Withdraw (DT&W) guideline that was effective in Jan 2013. Under the DT&W policy, it indicated that when a patient with RA who received 2 years biologics treatment with one of the following criteria: 1) disease activity score (DAS) $28 \leq 3.2$ or 2) erythrocyte sedimentation rate (ESR) $\leq 25\text{mm/h}$ and C-reactive protein (CRP) $\leq 1\text{mg/dL}$, the biological dose will be tapered to 50% less dosage and then be discontinued after one year of dose spacing. Full-dose biologicals can be re-applied only if a RA patient meets all of the following criteria after one year of dose spacing: (1) DAS28 raise > 1.2 ; (2) ESR $> 25\text{mm/h}$ and (3) ESR raise $> 25\%$.

The government aims to implement DT&W policy to reduce the total health care spending on the biologics. Although the policy was implemented since 2013, physicians as well as patients are generally reluctant to dose tapering. In this regard, it is acknowledged by both physician association and patients associations that there is an intense need to collect RWE to demonstrate the value of continued use of biologics as well as early biological treatment of RA patients to payers.

AbbVie collaborated with Taiwanese rheumatologists to implement the TAPER Study to assess the impact of DT&W policy on biological efficacy and social-economic endpoints by real-world chart review. The preliminary data was presented at the Asian Pacific League of Associations for Rheumatology (APLAR) 2015 Meeting. In addition, these data will be presented at the annual meeting of Taiwan Rheumatology Association

(TRA) in November 2015. We also plan to share the preliminary results of TAPER Study with the review committee of the BNHI to strengthen the importance of continuing biological therapy in RA patients and aim to loosen the DT&W guideline in Taiwan. This is a good example of local public health policy probably being influenced by the RWE.

Considering the particular reimbursement policy in Taiwan, having the more “real world evidence” (RWE) of local economic and health outcomes for the use of adalimumab in moderate to severe RA patients will be more valuable to support the reimbursement / pricing maintenance in Taiwan.

The objective of this non-interventional, observational study is to assess the effect of adalimumab on health-related QoL, work productivity, and healthcare resource utilization (HCRU) in patients with RA in Taiwan.

8.0 Research Question and Objectives

The objective of this study is to assess the effect of adalimumab on health and disability outcomes in patients with the immune-mediated inflammatory diseases of rheumatoid arthritis using the real world data as observed. The effect of adalimumab on health and disability outcomes in these patients will be assessed by the primary outcome measure which is the change in Health Assessment Questionnaire Disability Index (HAQ DI) score at 24 weeks after the initiation of adalimumab. The HAQ DI is selected as the primary point as it is commonly used to assess improvements in physical function in RA clinical trials and recommended by the US Food and Drug Administration (FDA) guidance on RA treatment development (3, 4). In addition, the HAQ-DI has been utilized as a predictor variable in investigations of productivity (5). The HAQ-DI has been demonstrated to be significantly correlated with work-related measures such as work capacity, household work performance, work task performance, and work disability (6-9). In addition, the effect of adalimumab will also be assessed by the secondary outcome measures which are changes to the WPAI, EuroQol 5 dimension (EQ-5D) score, and Short Form 36-Item Health Survey (SF-36) domain scores at 12 and 24 weeks after the initiation of adalimumab in RA.

8.1 Safety Information

Adalimumab therapy has a well-established and well described safety profile based on extensive postmarketing experience and continued clinical trial patient exposure since the first approved indication in 2002 for rheumatoid arthritis. AbbVie is committed to continue to collect safety information including those events that may occur in this trial in order to confirm this established safety profile and to identify any unknown potential adverse reactions, rare events and those events with a long latency. AbbVie is

participating in an FDA-requested, TNF inhibitor class wide exploration of the rare appearance of malignancy in subjects/patients who are 30 years of age or younger at the time of diagnosis. The risk of malignancy in this age group has not been established and is difficult to study due to its rarity. AbbVie appreciates your attention to the additional reporting requirements needed in this unlikely event, outlined in Section 11.1.5 under Adverse Event Reporting.

9.0 Research Methods

9.1 Study Design

This study is designed as a prospective, observational study to assess the effect of adalimumab on health-related QoL and work productivity in patients with RA in Taiwan in clinical practice.

Note: This study is non-interventional and the subjects/investigators will follow the current clinical practice in each site and also the routine clinical follow up as determine by the treating physician.

This study is non-interventional. Patient therapy is not decided by the study protocol but falls within current medical practice, and the prescription of adalimumab is clearly separated from the decision to include the patient in this study. The subjects/investigator will follow the current clinical practice in each site and also the routine clinical follow up as determine by the treating physician.

RA patients will be recruited from within the clinical settings of each rheumatologist participating in the study. Approximately 100 patients diagnosed with RA that meet the inclusion and exclusion criteria will be enrolled at approximately 7 sites in Taiwan.

To assess health and disability outcomes, the HAQ DI at baseline, Week 12 and Week 24 after treatment initiation with adalimumab will be collected. In addition, other PROs of work activity and well-being, including the WPAI, EQ-5D, and SF-36, will also be collected. All above instruments have been validated for the Chinese version.

The HCRU will also be collected. This includes surgical procedures, hospitalizations, bed days in hospital, physician consultations etc. Costs will be assigned based on the HCRU using standardized costs for each participating centers.

The patients identified by the recruiting investigators based on the study selection criteria will be collected data as observed on QoL, functioning, work productivity,

treatment satisfaction, impression of change and HCRU. Data will be captured at baseline (D0), Week 12 and Week 24.

Subjects may discontinue adalimumab treatment at any time during study participation. Subjects that end study participation early will have a Termination Visit, which may be a routine follow-up visit at investigator's clinic. All subjects will have a data recorded approximately 70 days after the Week 24 dosing or after the last administration of adalimumab to obtain information on any new or ongoing AEs.

Primary Endpoint Analysis

Change in HAQ DI score at 24 weeks after the initiation of adalimumab, in those patients continuing on adalimumab (as observed population). This change will be summarized as the mean and 95% confidence interval and will be tested with a paired t-test.

Secondary Endpoint Analysis

- Change in HAQ DI score at 12 weeks after the initiation of adalimumab, in those patients continuing on adalimumab (as observed population). This change will be summarized as the mean and 95% confidence interval and will be tested with a paired t-test.
- Change in other patient reported outcomes (SF-36 domain scales, EQ-5D Index, WPAI total lost productivity) at weeks 12 and 24 after the initiation of adalimumab, in those patients continuing on adalimumab (as observed population). These changes will be summarized as the means and 95% confidence intervals and will be tested with paired t-tests.
- Number and percent of patients achieving a clinically meaningful improvement on the HAQ DI, as defined by a -0.22 point improvement or greater, at weeks 12 and 24 after the initiation of adalimumab, in those patients continuing on adalimumab (as observed population).

Exploratory Endpoint Analysis

- Change in HAQ DI score at 24 weeks after the initiation of adalimumab, in those patients continuing on adalimumab (as observed population), compared with those patients not continuing on adalimumab (withdrawal population). The mean changes in these two groups will be compared using an independent t-test.
- Healthcare resource utilization will be described using number and percentage within each category (number of consultations, number of procedures received, number of surgeries, number of hospitalizations and length of stay, number of concomitant medications)
- Change in patient satisfaction questions at weeks 12 and 24 after the initiation of adalimumab, in those patients continuing on adalimumab (as observed population). These changes will be summarized as number and percentage of

each response and compared with Kruskal–Wallis test. Satisfaction will also be dichotomized and analyzed over time with Cochrane–Armitage test for trends.

- Patient's impression of change at weeks 12 and 24 after the initiation of adalimumab, in those patients continuing on adalimumab (as observed population). These changes will be summarized as number and percentage of each response and compared with Kruskal–Wallis test.
- Associations between disease severity and PROs
- Associations between change in disease severity and change in PROs

Observation period

- Observation of safety till 70 days after the Week 24 dosing or after the last dose of adalimumab
- Observation of pregnancy till 150 days after the Week 24 dosing or after the last dose of adalimumab

9.1.1 Schedule of Events

Table 1 Data Collection/Observation

	Data Collection/Observation	Baseline ^a ± 7 days	Week 12 (V2) ± 7 days	Week 24 (V3) ± 7 days	Early Termination / Drop out	70 days after the Week 24 or the last dose	150 days after the Week 24 or the last dose
Clinician Packet	Inclusion/exclusion form	X					
	Clinical history/patient demographics	X					
	Comorbidities	X					
	DAS28 (ESR) or DAS28 (CRP)	X	X	X	X		
Patient Packet	EuroQoL 5-Dimension (EQ-5D)	X	X	X	X		
	Short Form 36-Item Health Survey (SF-36)	X	X	X	X		
	Health Assessment Questionnaire (HAQ)	X	X	X	X		
	Work Productivity and Activity Impairment Questionnaire (WPAI)	X	X	X	X		
	Healthcare Resource Utilization (HCRU)	X	X	X	X		
	Patient Global Impression of Change (PGIC)		X	X	X		
	Patient Treatment Satisfaction Questions	X	X	X	X		
Clinicia	Adverse events	←				→	
	Pregnancy	←				→	

a. The Baseline will serve as the reference date for all subsequent time-points. A ± 7 day window is permitted around scheduled data collection time-points.

9.2

Setting

The study will take place in single country (Taiwan) with multiple centers. The study sites will be identified and selected by AbbVie. The study population shall comprise of male and/or female patients who are attending a routine clinical visit and meet all of the inclusion criteria and none of the exclusion criteria. Overall, approximately 100 subjects with clinically diagnosed RA are planned to be enrolled in the study at up to 7 sites.

The recruiting investigators will select potentially eligible patients from consecutive visits within their clinic based on the inclusion and exclusion criteria (Section 9.2.1 and Section 9.2.2). It is the responsibility of each physician to ask every consecutive patient who meets the inclusion criteria of the study to participate to avoid selection bias, and if investigators hold different types of clinics (e.g. routine visit clinics versus emergency clinics), only patients visiting their routine clinics will be used for patient selection.

Site personnel should thoroughly assess the eligibility criteria and evidence of this should be stored with the source documentation at site. Where there is any deviation from the inclusion/exclusion criteria, the patient should be excluded from the study.

Subjects that initially screen fail for the study may be permitted to re-screen following re-consent. All screening procedures with the possible exceptions noted below will be repeated. The subject must meet all inclusion and none of the exclusion criteria at the time of re-screening in order to qualify for the study. There is no minimum period of time a subject must wait to re-screen for the study. If the subject had a complete record of eligible criteria including a PPD test (or equivalent), or Interferon-Gamma Release Assay (IGRA; QuantiFERON-TB Gold In-Tube test or T-SPOT TB test), Chest x-ray (if applicable) and ECG no more than 3 months (90 days) have passed, these data will not be required to be repeatedly collected for re-screening. As appropriate, sites are encouraged to contact the AbbVie Medical Monitor to confirm if subjects should or should not be re-screened.

9.2.1 Inclusion Criteria:

Patients meeting all of the following inclusion criteria at baseline will be included:

1. Subject has a diagnosis of RA as defined by the 1987 revised ACR classification criteria and/or the ACR/ the European League against Rheumatism (EULAR) 2010 classification criteria (any duration since diagnosis)
2. Male or female subjects ≥ 18 years of age (local definition according to adalimumab label) who is in compliance with eligibility for adalimumab based on the local label
3. Patients with moderate to severe RA defined as DAS28 (ESR) or DAS28 (CRP) > 3.2

4. Biologically treatment naïve and initiated adalimumab at baseline visit
5. Availability of clinical data of the previous 12 weeks prior to baseline
6. Ability to self-complete patient questionnaires
7. Subject must be able and willing to provide written informed consent and comply with the requirements of this study protocol

Additional Inclusion Criteria

8. Female subjects who are either not of childbearing potential, defined as postmenopausal for at least 1 year or surgically sterile (bilateral tubal ligation, bilateral oophorectomy and/or hysterectomy) or are of childbearing potential and are practicing an approved method of birth control throughout the study and for 150 days after the Week 24 dosing or the last dose of adalimumab.
9. Subjects judged to be in good health as determined by the Principal Investigator based upon the results of medical history, laboratory profile, physical examination, chest x-ray (CXR), and a 12-lead electrocardiogram (ECG) performed no more than 3 months (90 days) have passed.
10. Subjects have negative TB Screening records. If a subject has evidence of a latent TB infection, the subject must initiate and complete a minimum of 1 month (per Taiwan guideline) of an ongoing TB prophylaxis or have documented completion of a full course of TB prophylaxis, prior to Baseline

9.2.2 Exclusion Criteria:

Patients meeting any of the following exclusion criteria at baseline will be excluded:

1. Patients who are pregnant or breast feeding at enrolment or wish to become pregnant in the next 24 weeks
2. Participation in any RA-related clinical trial at the time of enrolment, at baseline or at any point during the past 24 weeks prior to baseline
3. Patients, who in the clinician's view, may not be able to accurately report their QoL or prior resource utilization
4. Patients, who in the clinician's view, may not be able to adhere to adalimumab therapy over 24 weeks

Additional Exclusion Criteria

5. Subject has been treated with any investigational drug of chemical or biologic nature within a minimum of 30 days or five half-lives (whichever is longer) of the drug prior to the Baseline Visit
6. Infection(s) requiring treatment with intravenous (IV) anti-infectives within 30 days prior to the Baseline Visit or oral anti-infectives within 14 days prior to the Baseline Visit
7. Prior exposure to biologics that have a potential or known association with PML (i.e., natalizumab (Tysabri®) or rituximab (Rituxan®))
8. Known hypersensitivity to adalimumab or its excipients

9. History of demyelinating disease (including myelitis) or neurologic symptoms suggestive of demyelinating disease
10. History of invasive infection (e.g. listeriosis and histoplasmosis), human immunodeficiency virus (HIV)
11. Subjects with any active viral infection that based on the investigator's clinical assessment makes the subject an unsuitable candidate for the study
12. Hepatitis B: HBs Ag positive (+) or detected sensitivity on the HBV-DNA PCR qualitative test for HBc Ab/HBs Ab positive subjects
13. Chronic recurring infections or active TB
14. History of moderate to severe congestive heart failure (NYHA class III or IV), recent cerebrovascular accident and any other condition which would put the subject at risk by participation in the study
15. Evidence of dysplasia or history of malignancy (including lymphoma and leukemia) other than a successfully treated non-metastatic cutaneous squamous cell or basal cell carcinoma or localized carcinoma in situ of the cervix
16. Positive pregnancy test at Screening or Baseline
17. History of clinically significant drug or alcohol abuse in the last 12 months
18. Clinically significant abnormal screening laboratory results as evaluated by the Investigator

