9. Please check any Hylan G-F 20 (Synvisc) injection this patient has received for her/his Rheumatoid Arthritis in the last 6 months.

 No injection performed	Injection Place	Dosage	Number of Shots
 Yes →	 Hip	_____ ml	_____
	 Knee	_____ ml	_____

10. Please provide the dosing information for the first injection of Adalimumab (Humira) this patient has received for her/his Rheumatoid Arthritis.

First time administration (DD/MM/YYYY):	Dosage
____/____/____	_____ mg

1023259 Real-World Impact of RA
[REDACTED]
Site number - Participant ID

[figure not shown]
11. Please record the current medications this patient has received for her/his Rheumatoid Arthritis.

Drug Name	Average number of pills per day	Dose strength	Times per month
Disease Modifying Antirheumatic Drug (DMARD)			
 ₁ Auranofin (Ridaura, Myochrysine)	_____	_____ mg	_____
 ₂ Azathioprine (Imuran)	_____	_____ mg	_____
 ₃ Cyclosporine (Sandimmune and Neoral)	_____	_____ mg	_____
 ₄ Hydroxychloroquine (Plaquenil)	_____	_____ mg	_____
 ₅ Leflunomide (Arava)	_____	_____ mg	_____
 ₆ Methotrexate (Rheumatrex, Folex)	_____	_____ mg	_____
 ₇ Minocycline (Minocin, Dynacin and Vectrin)	_____	_____ mg	_____
 ₈ Sulfasalazine (Azulfidine)	_____	_____ mg	_____
 ₉ Others	_____	_____ mg	_____
Anti-inflammatory Drug (NSAID)			
 ₁₀ Ibuprofen (Advil, Motrin, Nuprin)	_____	_____ mg	_____
 ₁₁ Naproxen (Naprosyn, Anaprox, Aleve)	_____	_____ mg	_____
 ₁₂ Celecoxib (Celebrex)	_____	_____ mg	_____
 ₁₃ Aspirin (ASA)	_____	_____ mg	_____
 ₁₄ Diclofenac (Voltaren)	_____	_____ mg	_____
 ₁₅ Indomethacin (Indocid)	_____	_____ mg	_____
 ₁₆ Others	_____	_____ mg	_____
Others			
 ₁₇ Steroids	_____	_____ mg	_____
 ₁₈ Stomach or gastric medications	_____	_____ mg	_____

Thank you for completing the Clinician Case Report Form.
Please return this form to the IMS representative.

Follow-up:

1023259	Real-World Impact of RA
Site number	Participant ID

Clinician Case Report Form (Follow-up)

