Appendix D. Health Assessment Questionnaire Disability Index (HAQ DI)

HEALTH ASSESSMENT QUESTIONNAIRE (HAQ-DI)®

Name: _____ Date: _____

Please place an "x" in the box which best describes your abilities OVER THE PAST WEEK:

	WITHOUT ANY DIFFICULTY	WITH SOME DIFFICULTY	WITH MUCH DIFFICULTY	UNABLE TO DO
DRESSING & GROOMING				
Are you able to:				
Dress yourself, including shoelaces and buttons?				
Shampoo your hair?				
ARISING				
Are you able to:				
Stand up from a straight chair?				
Get in and out of bed?				
EATING				
Are you able to:				
Cut your own meat?				
Lift a full cup or glass to your mouth?				
Open a new milk carton?				
WALKING				
Are you able to:				
Walk outdoors on flat ground?				
Climb up five steps?				

Please check any AIDS OR DEVICES that you usually use for any of the above activities:

 Devices used for Dressing (button hook, zipper pull, etc.)	 Built up or special utensils	 Crutches
	 Cane	 Wheelchair
 Special or built up chair	 Walker	

Please check any categories for which you usually need HELP FROM ANOTHER PERSON:

 Dressing and grooming	 Arising	 Eating	 Walking
--	----------------------------------	---------------------------------	----------------------------------

Please place an "x" in the box which best describes your abilities **OVER THE PAST WEEK**:

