Appendix G. Work Productivity and Activity Impairment (WPAI)

**Work Productivity and Activity Impairment Questionnaire:
Rheumatoid arthritis V2.0 (WPAI:RA)**

The following questions ask about the effect of your rheumatoid arthritis on your ability to work and perform normal daily activities. *Please fill in the blanks or circle a number, as indicated.*

1. Please check your current employment status.

 1	Full time (working for pay)
 2	Part time (working for pay)
 3	Volunteering
 4	Stopped working because of my RA
 5	Stopped working for other reasons
 6	Retired

If your response is 1 or 2, continue the survey.

If your response is 3-6, skip to question 6.

The next questions refer to the past seven days, not including today.

2. During the past seven days, how many hours did you miss from work because of problems associated with your rheumatoid arthritis? *Include hours you missed on sick days, times you went in late, left early, etc., because of your rheumatoid arthritis. Do not include time you missed to participate in this study.*

_____ HOURS

3. During the past seven days, how many hours did you miss from work because of any other reason, such as annual leave, holidays, time off to participate in this study?

_____ HOURS

[figure not shown]
4. During the past seven days, how many hours did you actually work?

_____ HOURS (If "0", skip to question 6.)

5. During the past seven days, how much did your rheumatoid arthritis affect your productivity while you were working?

Think about days you were limited in the amount or kind of work you could do, days you accomplished less than you would like, or days you could not do your work as carefully as usual. If rheumatoid arthritis affected your work only a little, choose a low number. Choose a high number if rheumatoid arthritis affected your work a great deal.

Consider only how much rheumatoid arthritis affected productivity while you were working.

[figure not shown]

CIRCLE A NUMBER

6. During the past seven days, how much did your rheumatoid arthritis problems affect your ability to perform your normal daily activities, other than work at a job?

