3.3.2 Data Collection

IMS will coordinate data collection with each site. At study initiation (Baseline, D0), patients will be asked to provide their written informed consent. After signing consent, the patients' questionnaires as recorded will be collected. At Week 12 and 24 time-points, the patients' questionnaires will be collected before them visiting their physicians. There will be a study coordinator or study nurse at each site to monitor the process. The study coordinator/nurse will collect the record of questionnaires directly. Physicians will not see the contents patients entered. The study coordinator/nurse will check to ensure all the forms are filled-in correctly.

In addition, physicians will also be asked to complete a clinical CRF in paper form based on the patient's medical records at baseline, 12 weeks, and 24 weeks. The CRF completed by physicians will be returned to the study coordinator/nurse at each site as well.

All data will be collected by the study coordinator/nurse at each site and returned directly to IMS. The data collection time is expected to be 10-13 months.

All patient and clinician data will be handled preserving confidentiality.

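### The ± 7 day window printed on the Baseline column of Table 1 admits questionnaires completed after the first adalimumab injection; any resulting bias is probably small and toward no change

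*Protocol*

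**What the plan says.** - **Window.** In Protocol 9.1.1, Table 1, the column head reads "Baseline ^a ± 7 days". Footnote a adds "The Baseline will serve as the reference date for all subsequent time-points" and then "A ± 7 day window is permitted around scheduled data collection time-points".
- **Treatment start.** Protocol 9.2.1, criterion 4: "Biologically treatment naïve and initiated adalimumab at baseline visit".
- **Day of baseline.** Protocol 9.1 and 9.2.4.6 and SAP 3.1 and 3.3.2 all call baseline D0. The protocol abstract has the patient-reported data collected when adalimumab is initiated.
- **Order of events.** Protocol 9.2.4.6 and SAP 3.3.2 collect the baseline questionnaires after consent and do not mention the injection. The one ordering rule, "questionnaires will be collected before them visiting their physicians", covers Weeks 12 and 24.
- **Recall.** HAQ-DI (Appendix D) asks for the answer "which best describes your abilities OVER THE PAST WEEK". WPAI (Appendix G) states "The next questions refer to the past seven days, not including today". EQ-5D (Appendix F) asks about the day of completion. SF-36 mainly recalls four weeks (Protocol 9.2.4.7).
- **First-dose date.** The baseline CRF (Appendix C, item 10) records "First time administration (DD/MM/YYYY)".
- **SAP definition.** SAP 2.1 equates baseline with initiation of adalimumab. SAP 3.5 has no visit-window rule, no requirement that baseline precede the first dose, and no handling for a baseline that does not.

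**The concern.** This is a single-arm before-after study, so the baseline value is the only comparator. It enters the primary HAQ-DI change, the count of patients improving by 0.22 or more, and the WPAI and EQ-5D changes. A form completed a few days after the first injection satisfies Table 1 and would be analysed as the pre-treatment value. If patients have begun to improve by then, part of the effect is already in the reference value and the measured change is too small. No control arm exists in which the same error could cancel.

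The instruments are not equally exposed. EQ-5D is affected by any post-dose completion. HAQ-DI and WPAI are affected in proportion to how much of the recall week follows the injection. For SF-36, at most about a quarter of the four-week recall period could be on treatment.

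**Working it through.** **1. Reproduce the planned power (Protocol 9.5).** Paired t-test, noncentral t, two-sided 0.05. Evaluable n = 100 × 0.9 = 90. For WPAI, n = 100 × 0.9 × 0.55 = 49.5, taken as 49.

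| Scenario | Planned | Recomputed |
|---|---|---|
| HAQ-DI change -0.21, SD 0.5, against 0 | at least 95% | 97.6% |
| HAQ-DI change -0.5, SD 0.7, against -0.22 | at least 95% | 96.4% |
| WPAI hours lost, change 10, SD 30 | 63% | 62.8% |

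The protocol's figures reproduce.

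**2. Recall overlap.** With the first injection on day 0, a form completed on day +k has about k of its 7 recall days on or after the injection, a share of k/7. At k = 7 the share is 1. If late forms were spread evenly over days +1 to +7 (assumption), the mean share is (1 + 2 + ... + 7)/(7 × 7) = 28/49 = 4/7, about 57%.

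**3. Size of the dilution.** Relative understatement = f × g × h, where

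- f = share of patients with a post-dose baseline: 20-50%, assumed;
- g = share of the Week 24 effect already present in week 1: 10-25%, assumed;
- h = recall exposure: 4/7 if spread evenly, 1 if every late form is fully exposed.

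Neither f nor g has a source in the documents.

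| f | g | h | Understatement | Of the planned 0.21 |
|---|---|---|---|---|
| 0.20 | 0.10 | 4/7 | 1.1% | 0.002 |
| 0.20 | 0.10 | 1 | 2.0% | 0.004 |
| 0.50 | 0.25 | 4/7 | 7.1% | 0.015 |
| 0.50 | 0.25 | 1 | 12.5% | 0.026 |

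**4. Effect on power.** Each planned mean change is multiplied by (1 - understatement), with the SD and n of step 1 kept. The WPAI rows carry the same assumptions over to hours lost.

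| Understatement | HAQ-DI -0.21 against 0 | HAQ-DI -0.5 against -0.22 | WPAI hours |
|---|---|---|---|
| 0 | 97.6% | 96.4% | 62.8% |
| 1.1% | 97.4% | 95.7% | 61.8% |
| 2.0% | 97.1% | 95.1% | 61.1% |
| 7.1% | 95.5% | 90.6% | 56.5% |
| 12.5% | 93.2% | 83.0% | 51.6% |

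The primary comparison against zero barely moves. The comparison against -0.22 is more sensitive because the margin it tests is only 0.5 - 0.22 = 0.28, so a loss proportional to 0.5 takes a larger part of it.

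**5. Cost of excluding post-dose baselines.** With f of 20-50%, 90 evaluable patients become 72 to 45. At a change of -0.21 and SD 0.5, power is 94.0% at n = 72 and 78.7% at n = 45.

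**The case against.** The strongest reply is that same-day collection was intended. Several sections fix baseline at D0, the abstract ties the questionnaires to initiation, and a window around the reference date itself makes little sense, so the ± 7 days may belong only to Weeks 12 and 24. That is probably the intent, and a reader should not infer that the plan calls for post-dose baselines. What remains is that the window is printed on the Baseline column, and nothing in either document closes its later side. Even D0 does not say before the injection.

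Three stronger readings are tempting and not supported:

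- **That all change scores are materially contaminated.** SF-36 mainly looks back four weeks, PGIC has no baseline assessment, and the ESR or CRP in DAS28 may be the latest value on record.
- **That the understatement is 12.5%.** That figure needs half the patients late, a quarter of the effect present in week 1, and every late form fully exposed. The first two have no source, and the third holds only at about day +7.
- **That defining baseline as the last value on or before the first dose would repair the data.** Table 1 schedules one baseline assessment, so there is no earlier value to substitute. Such a rule would only drop patients.

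**Conclusion.** The point holds as a gap in the timing rule: Table 1 as written admits on-treatment values as the baseline, against the evident intention of D0 collection. The documents do not allow the size to be fixed. Under the stated assumptions the change is understated by about 1-7% with late forms spread evenly over the week, and by 12.5% at most within those ranges. On the planned HAQ-DI change of -0.21 that is about 0.002 to 0.015, with a ceiling of 0.026. The direction assumes some benefit in the first week; without any, there is no bias of this kind. The bias runs toward no change and would not create a false positive, so a positive primary result is not in doubt. This is a minor point, worth correcting because the correction is cheap.

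**What to change.** **Protocol, Table 1.** Change the baseline window for the PROs and DAS28 to -7 to 0 days, completed before the first injection. This agrees with D0 and concerns only when data are collected. It costs one table cell and one sentence, and no change to sample size.

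**SAP, 3.5.** Flag and count patients whose baseline assessment is dated after the first-administration date on the CRF. Do not use a first-dose date whose day was imputed as 15 under SAP 3.5.5 for this classification; report those patients as unclassifiable. Keep flagged patients in the main analysis, and add a sensitivity analysis of the HAQ-DI change that excludes them. A form dated the same day as the injection cannot be ordered from dates alone, so the Table 1 rule is what protects those cases.

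**Cost.** The sensitivity analysis loses whatever share of patients has a post-dose baseline. If that share is small, little is lost; at the upper assumed share of 50%, power falls to about 79%, so the analysis should be read as a check on the estimate and not as a second test. The protocol planned to end data collection in January 2017, and the SAP's table-shell file names are dated January 2018. If collection is already complete, the Table 1 change comes too late, and only the SAP flag, count and sensitivity analysis can still help.
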